## 6.2 Eligibility criteria

#### 6.2.1 Inclusion criteria

- Aged 18 years or over
- Underlying pathology of leg ulcer is venous or mixed venous-arterial. Recognised comorbidities that may contribute to the development of leg ulcers (e.g. diabetes, rheumatoid arthritis, peripheral vascular disease) are not an exclusion criterion.
- At least one leg ulcer (in case of multiple defined ulcers, single largest measurable ulcer will be classed as index ulcer). Leg ulcer defined as any break in the skin on the lower leg that has been present for 2 weeks (from NICE 2013)
- Tolerating compression bandaging
- Mental ability to give consent
- An ankle–brachial pressure index (ABPI) of ≥ 0.5 0.8 taken within the previous 3 months. Where an ABPI measure is not viable, use of locally-approved alternative diagnostic assessments to rule out significant peripheral arterial disease and/or ischaemia, i.e. by pulse palpation and ultrasound diagnostics, toe pressure assessment or arterial imaging. If ABPI or other diagnostic methodology is not indicated or feasible, recorded clinical assessment by qualified clinical staff is allowed (diagnosis and rationale for reduced compression to be recorded at baseline).
- Patient is allowed to be on compression therapy prior to enrolment.

#### 6.2.2 Exclusion criteria

- Under the age of 18 years
- Unable to fully understand the consent process and provide informed consent due to either language barriers or mental capacity
- Limited life expectancy, i.e. undergoing palliative care, or other condition that in opinion of researcher contraindicates participation

- Active infection in leg ulcer treated with antibiotics within last 1 week (does not apply for prophylactic antibiotic regimes)
- Is not willing or able to wear any compression device
- Pure foot ulcer, ie any ulcer that commences below malleolar region (particularly plantar, digital regions)
- Enrolled in other interventional research study related to patient's leg ulcer
- Previous participation in PEACH trial
- Awaiting surgical intervention related to vascular system of the lower limbs, planned within three months
- Wound size that is too small (typically < 1 cm^2), or too large (larger than single wound grid or extending round the leg) to measure accurately
- Known intolerance or allergy to materials used in compression bandaging (including zinc oxide, calamine).

#### 6.3 Early withdrawal of subjects

Patients have the right to withdraw from the trial at any time and without giving any reason. If a patient withdraws from the trial, any and all information gathered prior to the withdrawal will be included in the analysis, though no further data collection will occur. If a patient does not attend planned follow-up appointments then two more attempts will be made to contact the patient regarding the study. If still no contact can be made then the patient is deemed lost to follow-up and any collected study data will be retained. Appendix 2, INTERVENTION DEVIATION AND LEG ULCER INFECTION, covers study withdrawals in more detail.

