## 8.2 Primary outcome statistics

The primary objective for this pilot study wound healed status at week 12. For non-inferiority analysis, patients who withdraw prior to completion of the study or do not attend week 12 appointment will be assigned the worst-case healing outcome (not healed at week 12).

The test for non-inferiority concerns the proportion of patients attaining ulcer closure by week 12 for both treatment groups, and the associated 97.5% one-sided confidence interval for the difference. Non-inferiority of Andoflex is considered valid if the lower limit of the 95% confidence interval for the difference between treatment means (Andoflex – Coban2) is not more negative than -15%. That is, non-inferiority for Andoflex is demonstrated when a maximum of 15% fewer patients using this bandage, compared with patients using Coban2, have healed by week 12 of treatment. This approach was taken in previous non-inferiority trials for ulcers (Harding et al, 2012; Moffatt et al, 2019), and is outlined in papers by Oczkowski (2014) and Flight (2016).

For comparative performance (superiority) analysis, any statistically significant difference (p-value < 0.05) between the two treatment arms will be determined with Chi-squared test. This will be done since Dunn et al postulate that non-inferiority and superiority trials effectively aim to answer the same hypothesis (Dunn et al, 2018)

Analysis will be performed on a per protocol and also an intention to treat basis. Multiple imputation (default five imputations) will be applied for missing values for the outcome measures, and inferential statistics will be performed on pooled data. Data will first be collated in Microsoft Excel, followed by analyses performed using SPSS v20.

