#### APPENDIX 2. INTERVENTION DEVIATION AND LEG ULCER INFECTION

There may be incidences where a participant may either:

- Develop a reaction to the allocated dressing/bandage
- Becomes completely non-compliant (possibly due to bandaging being uncomfortable, or eg hospital admission)
- Improve to such an extent that compression bandaging is no longer indicated.

In such instances the patient and/or clinician can opt to stop or pause treatment with the bandage in question. If this occurs, this needs to be recorded (date and reason), and the decision can then be made to either:

- Discontinuation due to improvement in symptoms (including wound healed). Participant will still continue to be assessed as per planned dates and timepoints.
- Change over to an alternative compression bandage that is not the originally allocated type. This is allowed but only if there are clinical indications to do so or at patient request if they cannot tolerate the allocated bandage type. Patient can later in trial period be transferred back to original allocated bandage type if required.
- Pausing or discontinuation of compression bandaging when not clinically indicated. Even if leg ulcer persists and patient no longer wears compression bandage, they can still continue in the trial if they wish. Outcome measures will continue to be recorded as per planned dates and timepoints.
- Pause of compression therapy due to adverse event. Patient can remain in trial provided they are capable to continue with follow-up schedule and completion of outcome measures. If not possible, see next point regarding 'Withdraw patient from study'.
- Withdraw patient from study.
  - At the request of the patient
  - For clinical reasons, eg if the leg has deteriorated to such an extent that emergency surgical or medical intervention is required which means return to use of compression bandage in reasonable time frame is not feasible. In this case, this needs to be reported as a (Serious) Adverse Event if discontinuation is due to deterioration of the index wound or index leg only.

When overall trial participation for a patient is finished early, the participant will still be asked to complete the relevant questionnaires (provided they have capacity to do so):

- Week 6 VEINES QoL questionnaire (if patient withdrawal before week 6)
- Week 12 VEINES QoL questionnaire (if patient withdrawal > week 6 and < week 12)

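### Section 6.3 and Appendix 2 conflict on data collection after withdrawal, and neither seeks week-12 ulcer status from patients who fully withdraw

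*Protocol*

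**What the plan says.** Protocol section 6.3 (Early withdrawal of subjects) states that, when a patient withdraws, "any and all information gathered prior to the withdrawal will be included in the analysis, though no further data collection will occur". It adds that Appendix 2 "covers study withdrawals in more detail", without saying which text prevails.

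Appendix 2 says: "When overall trial participation for a patient is finished early, the participant will still be asked to complete the relevant questionnaires". It lists only VEINES-QoL: "Week 6 VEINES QoL questionnaire (if patient withdrawal before week 6" and "Week 12 VEINES QoL questionnaire (if patient withdrawal > week 6 and < week 12". It gives no completion date and does not mention the wound.

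Appendix 2 treats patients who discontinue or pause compression but remain in the trial differently: "Outcome measures will continue to be recorded as per planned dates and timepoints".

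Section 8.2 (Primary outcome statistics) says that, for non-inferiority, "patients who withdraw prior to completion of the study or do not attend week 12 appointment" are given the worst-case result, not healed. The same section applies multiple imputation (five imputations) to missing outcome values and does not say how the two rules divide the cases.

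Sections 5.2 and 5.4 say that standard care is unaffected by withdrawal, and that the vascular or community nurse redresses and measures the ulcer as part of routine care.

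**The concern.** Two things look wrong. First, one passage forbids all collection after withdrawal and the other requests a questionnaire. Staff at different sites could follow either, and a withdrawing patient could be told either.

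Second, the only item requested after withdrawal is a secondary outcome. Healing status, on which the trial is decided, is not sought, although nurses will often still be seeing the leg. Under the non-inferiority rule an assumed failure takes its place. Read literally, that rule covers even a patient recorded as healed at week 6 who then withdraws.

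The same failure rule in both arms shrinks both healing rates and pulls them together. In a superiority trial that is usually cautious. In a non-inferiority trial it is not, because a true deficit also shrinks towards the margin. If withdrawal differs between arms, the bias can go in either direction. Participants are not blinded (section 6.1.1), and the introduction reports a difference in comfort and itch between the two brands, so equal withdrawal cannot be taken for granted.

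**Working it through.** **Inputs.** Section 6.1 and Table 4: healing 65% (Andoflex) and 50% (Coban2), margin 15 points, one-sided 2.5%, 80% power, 1:1 allocation, 10% dropout, 92 patients (46 per arm). Table 3 footnote: visits may be up to 2 weeks early or late.

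**Reproducing the plan's figure.** With the unpooled normal approximation, n per arm = (1.960 + 0.842)² × (0.65×0.35 + 0.50×0.50) / (0.15 + 0.15)² = 7.85 × 0.4775 / 0.09 = 41.6, so 42 per arm and 84 in total. Allowing for dropout, 84 × 1.10 = 92.4 and 84 / 0.90 = 93.3 (94 for equal arms). The stated 92 is reproduced within rounding.

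**How many are affected.** 92 × 0.10 = 9.2 patients. This is an upper figure, because the 10% also contains any other loss. If these patients healed at the planning rates, 4.6×0.65 + 4.6×0.50 = 5.3 healed ulcers would be scored as failures.

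**Effect of scoring withdrawals as not healed.** Observed rate = true rate × (1 − withdrawal rate). Chance of declaring non-inferiority = Φ[(0.15 + difference)/SE − 1.96], with SE = √[(pA(1−pA) + pC(1−pC))/46].

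- Status known for all 92: difference 0.150, SE = √(0.4775/46) = 0.1019, Φ(0.300/0.1019 − 1.96) = 83.8%.
- 10% withdrawn per arm: rates 58.5% and 45%, difference 0.135, SE = 0.1032, Φ(0.285/0.1032 − 1.96) = 78.8%.
- True 15-point deficit (35% v 50%), status known for all: 2.5%.
- The same with 10% withdrawn per arm: rates 31.5% and 45%, difference −0.135, SE = 0.1004, Φ(0.015/0.1004 − 1.96) = 3.5%.

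**Unequal withdrawal.** The splits are assumptions; the protocol gives only 10% overall.

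| Withdrawn, Andoflex / Coban2 | Difference, true 65% v 50% | Power | False non-inferiority, true 35% v 50% |
|---|---|---|---|
| 0% / 0% | 15.0 points | 83.8% | 2.5% |
| 10% / 10% | 13.5 points | 78.8% | 3.5% |
| 15% / 5% | 7.75 points | 59.1% | 1.3% |
| 5% / 15% | 19.25 points | 91.8% | 8.2% |

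**Questionnaire timing.** The week-12 window runs from week 10 to week 14. If a patient leaving in week 7 completed the form on leaving, the answer would come three weeks before the window opens. If the form were sent on the scheduled date, its timing would be right, but collection after withdrawal would then plainly break section 6.3.

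**The case against.** Appendix 2 can be read as the promised detail: a general rule with one voluntary exit questionnaire as an exception. That softens the conflict but does not remove it, since section 6.3 allows no exception. The clash itself touches only a secondary outcome.

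Stopping collection at a patient's request is a defensible consent choice. That stands for patients who refuse further data use. It does not explain why a patient who may still be asked for a questionnaire is not asked about the ulcer. Patients withdrawn because the leg deteriorated probably would not have healed, so the planning rates overstate what is lost.

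The power loss is small against the plan's own target. Analysing only 41 completers per arm would give about 79.4%, and 92 already allows for 10% attrition. The 5-point loss is relative to full ascertainment.

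Four stronger readings are tempting, and the protocol does not support them:

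- A reader might infer that everyone who comes off the allocated bandage loses the primary outcome. Appendix 2 provides for patients who stop, pause or switch to stay in follow-up, so only full withdrawal is at issue here.
- A reader might infer that observed week-12 results are discarded. After withdrawal before week 12 the status has not been observed. It is often obtainable, which is a weaker statement.
- A reader might infer that section 8.2 simply records all such patients as failures. That rule is stated for the non-inferiority analysis, and multiple imputation is named beside it. An analysis plan that is not at hand may settle how they divide.
- A reader might infer that early VEINES-QoL answers are analysed as week-6 or week-12 values. Appendix 2 gives no completion date and says nothing about their analysis, so this is only a possibility.

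**Conclusion.** The point holds in limited form. The conflict between section 6.3 and Appendix 2 is plain in the current text and must be reconciled. For full withdrawals, neither passage seeks the week-12 index-ulcer status, and the non-inferiority analysis puts an assumed failure in its place.

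At most about 9 of 92 patients are affected. On the upper-bound assumptions (all of the 10% are full withdrawals, equal in both arms, healing at the planning rates) the expected difference loses 1.5 points, power loses about 5 points relative to full ascertainment, and the false non-inferiority rate rises by about 1 point. These effects are modest. The larger ones, power of 59.1% or false non-inferiority of 8.2%, need unequal withdrawal, which the protocol does not predict but gives some reason to expect. What is collected after withdrawal, and with what consent, has to be settled in the protocol. The change is cheap and worth making.

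**What to change.** 1. Align section 6.3 and Appendix 2. Limit the ban on further collection to patients who refuse further data use.
2. For all other withdrawers, take index-ulcer status at week 12 from the routine nursing visit or record, subject to consent. Use it in the intention-to-treat analysis in place of the assumed failure.
3. In section 8.2, state which rule, not healed or multiple imputation, applies in which analysis to patients whose status is still missing.
4. Record the completion date of any exit questionnaire. If it lies outside the 2-week window either side of the visit, do not analyse it as the week-6 or week-12 value.

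The cost is a change to protocol and consent wording and one data item for at most about 9 patients. The consent pages were not available, so whether they already allow use of routine records after withdrawal has to be checked.

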#### Table 3. Baseline measures

# Allowed to be up to 2 weeks early or late. For all follow-up dates, calculation is based on original enrolment date for patient, even if deviation for one or more follow-up timepoints.

The Pressure Ulcer Scale for Healing (PUSH) tool, see Appendix 1 is a standardised method of assessing and monitoring the severity and healing of both pressure ulcers and venous leg ulcers (Stotts et al, 2001; Ratliff & Rodeheaver 2005). Concerns have been raised regarding the criterion validity and intra-rater reliability of the tool (Pillen et al 2009) however in the absence of other valid tools it provides a comprehensive parallel assessment of the ulcer along with measuring size alone.

VEINES-QoL is a patient reported outcome measure score that focuses on lower limb health, and can be used in patients both with, or without a leg ulcer (Launois 2015)

During the recruitment process the research team acts as a contact point and coordinator for patients requiring information and support. If concerns are raised on participants (mental) wellbeing

based on the home visits or outcome of the assessments, referral of patients/families on to other professional agencies will be done as appropriate and according to the Trust guideline.

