#### 5.4 Follow-up and Standard care

Patients are in the study for the planned 12 weeks, even if the index leg ulcer has healed prior to that time point. Apart from the specific research measurements and assessments, the patient will be followed up as they would in normal clinical practice. The vascular or community nurse will redress the leg ulcer as per routine care, and will conduct the measurement of the leg ulcer (grid measurement and PUSH score). The researcher will visit the patient at baseline, week 6 and 12 of study participation to randomise the patient and conduct the questionnaires.

Patients identified in the community (primary care or non-vascular surgery dept) can be invited to participate in the study via the vascular surgery department.

Standard wound care will be provided throughout the trial period, as well as meeting any other medical needs that arise. The SIGN guidelines for leg ulcer care form the framework for management of the leg ulcers (https://www.sign.ac.uk/media/1058/sign120.pdf).

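### Section 6.3 does not secure a week-12 attempt after a missed visit, and section 8.2 scores week-12 non-attendance as not healed even where routine care has recorded the ulcer's status

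*Protocol*

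**What the plan says.** Section 6.3 treats two groups differently. For patients who withdraw, "any and all information gathered prior to the withdrawal will be included in the analysis, though no further data collection will occur". For patients who simply do not turn up, "If a patient does not attend planned follow-up appointments then two more attempts will be made to contact the patient regarding the study", and then: "If still no contact can be made then the patient is deemed lost to follow-up and any collected study data will be retained". No visit and no number of missed visits is named.

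There are only two follow-up visits to miss. Section 5.4 states: "The researcher will visit the patient at baseline, week 6 and 12 of study participation to randomise the patient and conduct the questionnaires". The note under Table 3 allows two weeks either side and adds that "calculation is based on original enrolment date for patient, even if deviation for one or more follow-up timepoints".

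Section 8.2 sets the scoring. For the non-inferiority analysis, the worst-case outcome goes to patients who withdraw early and to those who "do not attend week 12 appointment will be assigned the worst-case healing outcome (not healed at week 12". Later in the same section: "Multiple imputation (default five imputations) will be applied for missing values for the outcome measures".

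The ulcer itself is observed in routine care. Section 5.4: "The vascular or community nurse will redress the leg ulcer as per routine care, and will conduct the measurement of the leg ulcer". Appendix 2 keeps patients under assessment when the bandage is stopped, paused or changed. When participation ends early it asks for questionnaires (VEINES-QoL is listed) and does not list wound status.

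**The concern.** Week 6 is a planned follow-up appointment, so the section 6.3 rule can be applied there, six weeks before the primary outcome is due. Nothing in the section says that the week-12 visit is still attempted. Such a patient has not withdrawn, and the bar on further data collection is not written for them.

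In section 8.2 the trigger for the not-healed score is absence from a study appointment, not absence of information. If a treating nurse has recorded the ulcer as closed at about week 12 but the study visit was missed, the rule as written turns a known healed ulcer into a failure.

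The decision rests on a difference in healed proportions against a 15-point margin, and each patient is 1/46 = 2.2 points of an arm's rate. Scoring losses as failures in both arms multiplies both rates by the same factor and so shrinks the difference. In a superiority trial that is cautious. In a non-inferiority trial it moves a truly inferior bandage closer to the control. If losses differ between arms, which is possible because participants know their bandage, the difference shifts directly.

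**Working it through.** **Inputs.** From section 6.1 and Table 4: healing 65% (Andoflex) and 50% (Coban2), margin 15 points, one-sided 2.5%, power 80%, attrition 10%, 46 per arm. The attrition rates other than 10%, and all the unequal splits, are assumptions chosen to show a range.

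**The plan's own figure.** n per arm = [0.65×0.35 + 0.50×0.50] × (1.960 + 0.842)² / (0.15 + 0.15)² = 0.4775 × 7.849 / 0.09 = 41.6, so 42 per arm and 84 in total. With 10% attrition the unrounded total is 91.6 (×1.1) or 92.5 (÷0.9). The stated 92 reproduces.

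**Formula for power.** With rates p1 (Andoflex) and p2 (Coban2) and n = 46, SE = √{[p1(1−p1) + p2(1−p2)]/46} and power = Φ[(p1 − p2 + 0.15)/SE − 1.960]. If a fraction d is lost independently of healing and scored not healed, each rate becomes p(1 − d).

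**Every status known (d = 0).** SE = √(0.4775/46) = 0.1019. Power = Φ(0.30/0.1019 − 1.960) = 83.8%.

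**10% lost in each arm, all scored not healed.** The rates are 0.65×0.9 = 58.5% and 0.50×0.9 = 45.0%, a difference of 13.5 points. SE = √[(0.2428 + 0.2475)/46] = 0.1032. Power = Φ(0.285/0.1032 − 1.960) = 78.8%.

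**Range of equal loss.** At 5% power is 81.2%; at 20% it is 74.4%.

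**False non-inferiority.** Take a true difference of −15 points, 35% against 50%. With every status known the chance of declaring non-inferiority is 2.5%. With 10% loss the rates are 31.5% and 45.0%, the difference is −13.5 points, SE = √[(0.2158 + 0.2475)/46] = 0.1004, and the chance is Φ(0.015/0.1004 − 1.960) = 3.5%. At 20% loss it is 4.9%.

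**Unequal loss (assumed splits), true rates 65% and 50%.**
- 15% lost on Andoflex and 5% on Coban2: 55.25% against 47.5%, difference 7.75 points, power 59.1%.
- 5% lost on Andoflex and 15% on Coban2: 61.75% against 42.5%, difference 19.25 points, power 91.8%.

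All these figures assume that every lost patient is a non-withdrawn patient whose status could have been obtained.

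**The case against.** A reader might infer that section 6.3 closes a patient after one missed visit, even at week 6, so that the week-12 outcome is never sought. The text does not go that far. It speaks of appointments in the plural, names no number or week, and bars further data collection only for withdrawn patients. The Table 3 note, which keeps later dates running from enrolment after a deviation, sits more easily with continued follow-up, although it governs timing and does not reopen a patient already deemed lost. What stands is that the section is silent on the week-12 attempt.

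A reader might also infer that the rule penalises healing, because healed patients drop out of contact. Section 5.4 keeps patients in for the full 12 weeks after healing, and Appendix 2 continues their planned assessments. It also expects hospital admission and lets patients whose bandaging is paused remain in the trial. The documents give no evidence that healed patients are harder to reach.

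Nor do they show that most unreachable patients would have a week-12 nursing entry. The seven-day figure in the device descriptions concerns sustained compression, not a visit schedule. Section 8.1 lists self-care at home as one location of leg care, and Table 3 schedules ulcer measurement only at weeks 0, 6 and 12. Someone the study cannot reach may have left routine care too.

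Section 8.2 also contains the multiple-imputation sentence, so not-healed scoring is not its only provision for missing outcomes. The worst-case rule is, however, the one tied specifically to the non-inferiority analysis, and neither provision brings in a status observed in routine care.

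Finally, section 6.1 describes the 10% as patients who may withdraw, whereas this point concerns those who do not. Applying all of it here gives only an upper bound, and 78.8% is about one point below the planned 80%. That stands, and it limits the size claimed.

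**Conclusion.** The point holds in a limited form. Section 6.3 leaves open whether week 12 is attempted after a missed week 6, and section 8.2 ties the not-healed score to study attendance although the ulcer is observed in routine care. Followed as written, section 8.2 misclassifies a non-withdrawn patient whose healed status is on record.

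Within the planned attrition, the upper bound under equal loss unrelated to healing is a fall from 15 to 13.5 points in the expected difference, from 83.8% to 78.8% in power, and a rise from 2.5% to about 3.5% in false non-inferiority (control 50%). Unequal loss could do more, but no particular imbalance can be predicted from the protocol. The true effect depends on two unknowns: how many non-withdrawn patients cannot be reached, and how many of those have a usable record. The change is worth making because it is cheap and protects the primary outcome, not because a large bias has been shown.

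**What to change.** In section 6.3, state that a missed week-6 visit does not end follow-up and that the week-12 visit is attempted for every patient who has not withdrawn.

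In section 8.2, for non-withdrawn patients who miss week 12, use a healed or not-healed status recorded in routine care within the existing window (week 12 plus or minus 2 weeks), provided it meets the section 5.5.1 definition, and flag it as record-derived. Count an earlier closure entry only if the record also shows no recurrence up to that window: section 8.2 refers both to closure by week 12 and to status at week 12, and section 8.1 asks about recurrence after healing at week 6. Apply the section 8.2 missing-data rule only when no such record exists. Add a sensitivity analysis that leaves out record-derived outcomes.

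The cost is protocol wording and a short review of existing notes, for at most about 9 patients if attrition runs as planned (10% of 92 = 9.2). The downside is that these outcomes are unblinded and less detailed than a study assessment, and may not mention scab or dressing. The flag and the sensitivity analysis let a reader see how much the result depends on them.
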